2.8.4 Other safety data

2.8.4.1 ECG and cardiac imaging data

A standard 12-lead ECG is to be performed at screening. Tracings must be dated and signed by the investigator (or his/her designee) and filed with the subject's source documentation.

Results from 12-lead ECG should be captured on the ECG Evaluation CRF. Significant findings must be recorded as Relevant Medical History.

Data from electrocardiogram will be listed at screening and unscheduled visits.

2.8.4.2 Vital signs

Vital sign assessments are performed in order to characterize basic body function. The parameters collected are height (cm), weight (kg), body temperature (°C), respiratory rate (breaths per minute), pulse (beats per minute) and both systolic and diastolic blood pressure (mmHg).

The criteria for clinically notable abnormalities are defined below in Table 2-1.

The following summaries will be produced for each vital sign parameter:

- Number and percentage of patients with at least one post-baseline vital sign abnormality (in both directions, i.e., both elevated and below normal values).

In addition, the following two listings will be produced:

- Patients with clinically notable vital sign abnormalities.
- All vital sign assessments listed by patient and vital sign parameter.

In both listings, the clinically notable values will be flagged and the assessments collected later than 30 days after the last treatment date will also be flagged.

Table 2-1 Clinically notable values for vital signs

Vital Sign	Criteria for clinically notable abnormalities	
Systolic BP (mmHg)	High	≥ 180 mmHg and increase ≥ 20 mmHg from baseline
	Low	≤ 90 mmHg and decrease ≥ 20 mmHg from baseline
Diastolic BP (mmHg)	High	≥ 105 mmHg and increase ≥ 15 mmHg from baseline
	Low	≤ 50 mmHg and decrease ≥ 15 mmHg from baseline
Body temperature (°C)	High	$\geq 39.1^\circ\text{C}$
	Low	$\leq 35.0^\circ\text{C}$
Weight (kg)	High	Increase from baseline of $\geq 10\%$
	Low	Decrease from baseline of $\geq 10\%$
Pulse (beats per minute [bpm])	High	≥ 120 bpm with increase from baseline of ≥ 15 bpm
	Low	≤ 50 bpm with decrease from baseline of ≥ 15 bpm

2.8.4.3 WHO performance Status

The WHO performance scale (Table 2-2) is an instrument designed by the World Health Organization and is used to describe the physical health of patients, ranging from 0 (most active) to 4 (least active).

Table 2-2 WHO Performance Scale

Score	Description
0	Able to carry out all activity without restriction.
1	Restricted in physically strenuous activity but ambulatory and able to do light work.
2	Ambulatory and capable of all self-care but unable to carry out any work. Up and about more than 50% of waking hours.
3	Capable of only limited self-care, confined to bed or chair more than 50% of waking hours.
4	Completely disabled. Cannot carry on any self-care. Totally confined to bed or chair.

The WHO performance status will be analyzed for patients from the safety set. Frequency counts and percentages will be used to summarize performance status descriptively over time. A Listing of performance status will be presented.

2.8.4.4 Pulmonary function test

Change from baseline in pulmonary function tests by time point will be presented. Lung function parameters including FEV1, FVC and DL_{CO} and changes from baseline will be summarized descriptively (mean, standard deviation, 25th and 75th percentiles, median, minimum and maximum) at each assessment in sporadic LAM and LAM patients only from safety set. Listing of pulmonary function test will also be presented for LAM patients.

2.9 Pharmacokinetic endpoints

Not applicable

2.10 PD and PK/PD analyses

Not applicable

2.11 Patient-reported outcomes

Not applicable

2.12 Biomarkers

Not applicable

2.13 Other Exploratory analyses

Not applicable

2.14 Final analysis

A final analysis will be performed after all patients have completed Week 48 (or discontinued earlier but were followed up for efficacy up to Week 48) and their safety follow-up visit.

3 Sample size calculation

Approximately 40 patients will be enrolled to meet the CFDA post approval requirements. The sample size is based on feasibility, there is no hypothesis testing.

4 Change to protocol specified analyses

No change to protocol.

5 Appendix

5.1 Imputation rules

5.1.1 Study drug

The following rule should be used for the imputation of date of last administration for a given study treatment component:

Scenario 1: If the date of last administration is completely or partially missing and the end of treatment (EOT) eCRF page is available (prior to any death date or withdrawal of consent date, if available):

Case 1: The date of last administration is completely missing, and the EOT visit date is complete, then this latter date should be used.

Case 2: Only Year(yyyy) of the dose end date is available and yyyy < the year of EOT date:

Use Dec31yyyy

Case 3: Only Year(yyyy) of the dose end date is available and yyyy = the year of EOT date:

Use EOT date

Case 4: Both Year(yyyy) and Month (mm) are available for the date of last administration, and yyyy = the year of EOT date and mm < the month of EOT visit:

Use last day of the Month (mm).

After imputation, compare the imputed date with the start date of that specific record, if the imputed date is < start date of that record

Use the start date of that record.

Subjects with missing start dates are to be considered missing for all study treatment component related calculations described in Section 2.4.1 and no imputation will be made. If the date of first administration is missing, then the date of last administration should not be imputed.

5.1.2 AE date imputation

Adverse event end date

No imputation of partial date or missing date was done except for imputation to handle events spreading over the cut-off date.

Adverse event start date

If the adverse event start date was missing no imputation was done.

If the adverse event start date was partial (missing day) and the month occurred prior to the study medication start month and the year occurred prior to the study medication start year, the 15th of the specified month was used.

If the adverse event start date was partial (missing day), and the adverse event start month was greater than or equal to the study medication start month and the adverse event start year was greater than or equal to the study medication start year, the maximum of the first of the month of the adverse event start date or the study medication start date plus one day was used.

The table below presents the algorithm used to impute the partial AE start date:

	MON MISSING	MON < TRTM	MON = TRTM	MON > TRTM
YYYY MISSING	_null_	_null_	_null	_null_
YYYY < TRTY	01JULYYYY	15MONYYYY	15MONYYYY	15MONYYYY
YYYY = TRTY	TRTSTD+1	15MONYYYY	MAX(01MONYYYY, TRTSTD+1)	MAX(01MONYYYY, TRTSTD+1)
YYYY > TRTY	01JANYYYY	MAX(01MONYYYY, TRTSTD+1)	MAX(01MONYYYY, TRTSTD+1)	MAX(01MONYYYY, TRTSTD+1)

Where:

MON = Month of Partial Adverse Event Start Date

YYYY =Year of Partial Adverse Event Start Date

TRTM= Month of Treatment Start Date

TRTY= Year of Treatment Start Date

TRTSTD = Treatment Start Date

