2.1.1.6 On-treatment assessment/event

Adverse event summaries will present only on-treatment assessments, where on-treatment means that the AE started in the following time interval in the open-label period (including the lower and upper limits):

<date of first administration of open-label RAD001; date of last administration of open-label RAD001 + 30 days>.

Other safety summaries will present baseline and on-treatment assessments, where on-treatment means that the assessment occurred in the following time interval in the open-label period (including the lower and upper limits):

<date of first administration of open-label RAD001 + 1; date of last administration of open-label RAD001 + 30 days>.

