2.5.1 Primary endpoint

The primary endpoints are incidence of adverse events and laboratory abnormalities. For further details, please see safety analyses in [section 2.8](#).

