2.5.3 Handling of missing values/censoring/discontinuations

Not applicable

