2.8.1 Adverse events

General rules for AE Reporting

AE summaries will include all AEs starting on or after treatment day 1 (i.e., on or after the start date of everolimus) and no later than 30 days after the last day of everolimus. All AEs will be listed. AEs starting prior to treatment day 1 will be identified in the listings with a starting treatment day less than day 1, and AEs starting later than 30 days after the last day of everolimus will be specifically flagged.

AEs will be summarized by presenting the number and percentage of patients having at least one AE, and having at least one AE in each body system/primary system organ class, and for each preferred term using MedDRA coding. A patient with multiple occurrences of an AE will be counted only once in the AE category.

Separate AE summaries will be presented by primary system organ class, preferred term, and maximum common toxicity criteria (CTC) grade. A patient with multiple CTC grades for an AE will be summarized under the maximum CTC grade recorded for the event.

The frequency of CTC grade 3 and 4 AEs will be summarized separately.

Any information collected (e.g., CTC grades, relationship to study drug, action taken) will be listed as appropriate.

AE summaries

The following adverse event summaries will be produced:

- Adverse events, regardless of study drug relationship, by primary system organ class and preferred term
- Adverse events, with suspected relationship to study drug, by primary system organ class and preferred term
- Adverse events, regardless of study drug relationship, by preferred term
- Adverse events, regardless of study drug relationship, by primary system organ class, preferred term and maximum CTC grade
- Adverse events, with suspected study drug relationship, by primary system organ class, preferred term and maximum CTC grade

- CTC grade 3 or 4 adverse events, regardless of study drug relationship, by primary system organ class and preferred term
- CTC grade 3 or 4 adverse events, with suspected study drug relationship, by primary system organ class and preferred term
- Deaths, by primary system organ class and preferred term
- Serious adverse events, regardless of study drug relationship, by primary system organ class and preferred term
- Serious adverse events, with suspected study drug relationship, by primary system organ class and preferred term
- Adverse events leading to study drug discontinuation, regardless of study drug relationship, by preferred term

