2.8.1.1 Adverse events of special interest (AESI)/ grouping of AEs

For each specified AESI, the number and percentage of patients with at least one event of the AESI occurring during the on-treatment period will be summarized. Summaries of these AESIs will be provided grouped by CTCAE grades, SAE, relationship, leading to treatment discontinuation, leading to dose adjustment/interruption, etc.

Such groups consist of adverse events for which there is a specific clinical interest in connection with everolimus treatment (i.e., where everolimus may influence a common mechanism of action responsible for triggering them), or adverse events which are similar in nature (although not identical). A non-exhaustive list of AE groupings includes “Stomatitis and related events”, “Infections”, “Amenorrheas” and “Non-infectious pneumonitis”. All notable adverse event groupings are defined through the use of Standardized MedDRA Queries (SMQ), Preferred Terms (PT), High Level Terms (HLT), or System Organ Classes (SOC), or through a combination of these four components. At the project level, a SAS dataset named eCRS contains the exact composition of the adverse events groupings will be used to map reported adverse events to the notable adverse events groupings. This dataset may be updated (i.e., it is a living document) based on review of accumulating trial data, and it is the most up to date version at the time of DB lock that will be used. Note that certain adverse events may be reported within multiple groupings.

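### An adverse event with no start year has no route into the SAP's AE, SAE, Grade 3/4 or AESI tables, so AE incidence can be understated if any such record survives data queries

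*SAP*

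**What the plan says.** SAP 2.5.1 sets the primary endpoint: "The primary endpoints are incidence of adverse events and laboratory abnormalities".

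Three rules then decide whether an AE reaches a table.

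- **Dating (SAP 5.1.2).** "If the adverse event start date was missing no imputation was done". In the table for partial dates, the row for a missing year is null in every month column, so an AE with a known month but no year is also left undated.
- **On-treatment definition (SAP 2.1.1.6).** "Adverse event summaries will present only on-treatment assessments, where on-treatment means that the AE started in the following time interval", the interval running from first dose to last dose plus 30 days, both ends included.
- **Table inclusion (SAP 2.8.1).** "AE summaries will include all AEs starting on or after treatment day 1", with the same 30-day upper limit. SAP 2.8.1.1 counts patients "with at least one event of the AESI occurring during the on-treatment period".

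Two further statements bear on the effect. SAP 2.8.1 says "All AEs will be listed", so an undated record is still printed. It also says "A patient with multiple occurrences of an AE will be counted only once in the AE category".

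For the primary objective, the section "2.5.3 Handling of missing values/censoring/discontinuations" is marked as not applicable. SAP 2.5.4 leaves sensitivity analyses for missing assessments optional and does not mention undated AEs.

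**The concern.** A null date cannot be shown to lie in an interval. Taken together, the three rules keep an AE without a start year out of the AE tables, even if it was serious, judged drug-related or known to have ended during treatment. When such an AE did begin on treatment, leaving it out can only lower the reported incidence.

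This also sits oddly with the rest of the SAP. In SAP 5.1.2, an AE dated only to the year of first dose is set to first dose plus one day, and so counts as on-treatment. In SAP 5.1.3, a medication start date that cannot be placed before or after first dose is set before treatment only if the end date precedes treatment; otherwise it is set to the start of treatment. AEs with no start year have no comparable safeguard.

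The listings do not make the omission visible. SAP 2.8.1 identifies pre-treatment AEs by a treatment day below 1 and flags those starting more than 30 days after the last dose. An undated AE has no study day under SAP 2.1.1.4 and so carries neither mark.

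**Working it through.** The plan gives no figure to reproduce: the sample size rests on feasibility, with no hypothesis test (SAP 3), and no count of undated AEs is reported.

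**Inputs**

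- N = 40 patients enrolled and treated (Protocol, Amendment 2 rationale).
- Each patient counts once per row (SAP 2.8.1).
- The disclosure table of non-serious AEs has a 5% threshold (SAP 2.8.1), which is 2 of 40.
- Stomatitis occurred in 42.9% in the pivotal study (Protocol 1.2.3), or about 17 of 40. It serves only to illustrate a common event.
- Assumed: k = 0 to 2 patients per row whose only record there is undated, or a share m = 0% to 5% of AE records undated.

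**Step 1: loss per patient.** Reported incidence = (x − k)/40, so each such patient costs 1/40 = 2.5 points. Intervals are exact (Clopper-Pearson) 95%.

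| True count x | k = 0 | k = 1 | k = 2 |
|---|---|---|---|
| 17 | 42.5% (27.0 to 59.1) | 40.0% (24.9 to 56.7) | 37.5% (22.7 to 54.2) |
| 2 | 5.0% (0.6 to 16.9) | 2.5% (0.1 to 13.2) | 0% (0 to 8.8) |

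With x = 2, losing one patient also takes the event below the 5% threshold.

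**Step 2: expected loss.** If a patient has r records in the row and records are undated independently, expected loss = p × m^r. For p = 42.5%:

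| Share undated m | r = 1 | r = 2 |
|---|---|---|
| 1% | 0.43 points | 0.004 points |
| 2% | 0.85 points | 0.02 points |
| 5% | 2.13 points | 0.11 points |

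For any AE at 100% with five records per patient and m = 5%, the loss is 100 × 0.05^5, below 0.001 points. The effect is therefore confined to rows in which patients have a single record, which in practice means rare events.

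**Step 3: chance of missing the 5% threshold.** For an event in 2 of 40 patients with one record each, the chance is 1 − (1 − m)². This gives 2.0%, 4.0% and 9.8% at m = 1%, 2% and 5%.

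**Step 4: is on-treatment the better default?** AEs are collected from consent (Protocol 8.1.1). Assume up to 28 days of screening, 336 days of treatment, 30 days after last dose, a further 7 days for the follow-up visit window (Protocol Table 7-1), and a constant AE rate. The on-treatment share of collection time is then (336 + 30)/(28 + 366 + 7) = 366/401 = 91%. For a patient stopping at 12 weeks it is (84 + 30)/(28 + 114 + 7) = 114/149 = 77%. Under that assumption, exclusion is more often the wrong guess than the right one.

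**The case against.** A reader might infer that AEs with missing dates drop out of every on-treatment summary and that the primary incidence is therefore too low. The documents do not support either statement.

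- **Scope.** Laboratory abnormalities, the other primary endpoint, do not use AE start dates. Nor do vital signs, and the separate death summaries in SAP 2.8.2 state no AE-start condition.
- **Conditions.** A loss needs an AE that still has no start year after queries, truly began on treatment, and is the patient's only record in the row. The documents report no such AE and make one unlikely. Start dates are to be determined for each AE as far as possible (Protocol 8.1.1) and missing values are queried (Protocol 9.4). SAEs are reported within 24 hours (Protocol 8.2.2), and their documentation is fully verified (Protocol 9.2).
- **Pre-treatment events.** Some undated AEs may have begun between consent and first dose. Leaving those out is correct.
- **Silence.** The SAP does not say in terms that undated AEs are excluded. SAP 2.8 limits safety tables by when data were collected, and SAP 2.8.1.1 speaks of events occurring, not starting, on treatment.

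The first three points stand and limit the size of the issue. The fourth stands only in part. The collection limit in SAP 2.8 is an outer bound that does not replace the start-date test. SAP 2.1.1.6 restricts AE summaries to events that started in the interval, and no fallback is given. A programmer following the text would exclude the record.

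**Conclusion.** The concern holds as a gap in the classification rule, with an effect that is possible but not shown. Under the SAP as written, an AE without a start year cannot enter the AE, SAE, Grade 3/4 or AESI tables. Any resulting error lowers incidence, by 2.5 points in a row for each patient whose only record there is undated and truly on-treatment. On the assumed range of 0 to 2 such patients, the shift is 0 to 5 points in that row; common rows with repeat records and the overall any-AE row barely move. The true number is not given and may be zero.

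It would go too far to say that the primary safety result is understated or that the plan is wrong as written. That would need at least one record meeting all the conditions above, and the documents show none. This is a cheap improvement to part of the primary endpoint.

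**What to change.** In SAP 5.1.2, 2.1.1.6 and 2.8.1, state that an AE with a missing start year is classified as treatment-emergent unless its known end date, full or partial, shows that it ended before first dose. No start date need be invented for display; the rule serves classification only. Flag these records in the AE listing and report how many there are, including when the number is zero.

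The cost is a sentence or two in the SAP and a small addition to the derivation. SAP 2.7.1 already discusses what was seen at database lock, so the sponsor can count the records directly. The downside is that a few pre-treatment AEs may be counted as treatment-emergent, particularly as SAP 5.1.2 generally does not impute AE end dates, so incidence may look slightly less favourable. The flag and the count let a reader judge that. If there are no such records, no table changes.

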4. Action taken with respect to study or investigational treatment (none, dose adjusted, temporarily interrupted, permanently discontinued, unknown, not applicable)
5. Whether medication or therapy was given (no concomitant medication/non-drug therapy, concomitant medication/non-drug therapy)
6. Whether it is serious, where a serious adverse event (SAE) is defined as in [Section 8.2.1](#) and which seriousness criteria have been met

7. Outcome (not recovered/not resolved, recovered/resolved, recovered/resolved with sequelae, fatal, unknown)

If the event worsens the event should be reported a second time in the CRF noting the start date when the event worsens in toxicity. For grade 3 and 4 adverse events only, if improvement to a lower grade is determined a new entry for this event should be reported in the CRF noting the start date when the event improved from having been Grade 3 or Grade 4.

All adverse events should be treated appropriately. If a concomitant medication or non-drug therapy is given, this action should be recorded on the concomitant medication CRF.

Once an adverse event is detected, it should be followed until its resolution or until it is judged to be permanent, and assessment should be made at each visit (or more frequently, if necessary) of any changes in severity, the suspected relationship to the study treatment, the interventions required to treat it, and the outcome.

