10.4.2 Adverse events (AEs)

Summary tables for adverse events (AEs) will include only AEs that started or worsened during the Open-label Treatment phase, the *treatment-emergent* AEs.

The incidence of treatment-emergent adverse events (new or worsening from screening) will be summarized by system organ class and/or preferred term, severity (based on CTCAE version 4.03), type of adverse event, relation to study treatment

Serious adverse events, non-serious adverse events and adverse events of special interest (AESI) during the on-treatment period will be tabulated.

All deaths (on-treatment and post-treatment) will be summarized.

All AEs, deaths and serious adverse events (including those from Screening phase and 30 days safety follow-up visit) will be listed and those collected during the pre-treatment and post-treatment period will be flagged.

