5.1.3 Concomitant medication date imputation

Medication/therapy end date

If the medication/therapy end day or day/month was missing and the partial date indicated that the medication/therapy clearly started prior to or equal to the year of study treatment start - Impute the last day of the month or 31 December.

If the medication/therapy end date is completely missing - Check to see if medication is still ongoing before imputing a date and also when it started in relation to study drug. If the ongoing flag is missing then we assume that medication is still being taken (i.e. no imputation is done).

If the medication is not ongoing and medication start date is prior to first dose date of study treatment then impute the study treatment end date as medication end date. Similarly, if medication started on or after first dose date then impute the last date of either the last dose date of study treatment or a day after medication/therapy start date.

Medication/therapy start date

If the medication/therapy start day or day/month was missing and the partial date indicated that the medication/therapy clearly started prior to or equal to the year of study treatment start, the 1st of the month or January 1 was used as the medication/therapy start date.

If the medication/therapy start day was missing, and the partial date did not indicate if the date was before or after first dose of study treatment, the medication/therapy start date was imputed to:

- 01JAN CMDEND1Dyyyy if the medication/therapy end date was before the start of study treatment (where CMDEND1D is the medication/therapy end date).
- Start of study treatment otherwise.

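### SAP 5.1.2 can move an adverse event that ended before first dose into the on-treatment period, and SAP 2.8.1 counts improvement records of pre-dose Grade 3/4 events

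*SAP*

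**What the plan says.** SAP 2.5.1 makes AE incidence part of the primary endpoint: "The primary endpoints are incidence of adverse events and laboratory abnormalities". Whether an AE enters the tables depends on its start date alone. SAP 2.1.1.6 says "on-treatment means that the AE started in the following time interval in the open-label period", which runs from first dose to 30 days after last dose. SAP 2.8.1 repeats this: "AE summaries will include all AEs starting on or after treatment day 1", with the same upper limit.

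For a missing start day in the treatment-start month, SAP 5.1.2 uses "the maximum of the first of the month of the adverse event start date or the study medication start date plus one day". The table below that text gives first dose plus one day when only the year is known and it is the treatment year. Nothing in the rule refers to the AE end date.

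The protocol defines emergence differently. Section 10.4.1 sets three non-overlapping periods, and the pre-treatment one runs from consent to the day before first dose. Section 10.4.2 says the summary tables "will include only AEs that started or worsened during the Open-label Treatment phase". Section 8.1.1 adds a recording convention for Grade 3 and 4 events: "if improvement to a lower grade is determined a new entry for this event should be reported in the CRF", with its own start date. SAP section 4 declares no change from the protocol.

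**The concern.** AEs are recorded from consent, so some records will describe events that began before dosing. Treating an uncertain onset as on-treatment is a normal cautious convention. It has no purpose once a known end date shows that the event was over before the first tablet. Applying it there produces a record that starts after it ends and places a pre-treatment event in the primary incidence.

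The neighbouring rules do make this kind of check. SAP 5.1.1 compares an imputed last-dose date with the start date of the same record. For one class of partial medication start dates, SAP 5.1.3 applies a different value "if the medication/therapy end date was before the start of study treatment". Only the AE rule, which feeds the primary endpoint, lacks a check.

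The improvement records raise a related problem. An entry made because an event got better satisfies the SAP's start-date test, although it is neither a new event nor a worse one.

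**Working it through.** The plan gives no figure to reproduce. The sample size rests on feasibility (SAP section 3: "Approximately 40 patients will be enrolled to meet the CFDA post approval requirements"), and SAP 2.7.1 confirms 40 patients. The check applies the rules as written.

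**1. The formula in the dosing month.** Imputed start = max(first of AE month, first dose + 1). If the AE month and year are those of first dose, the first of the month is never later than first dose, so the result is always first dose + 1.

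**2. Test cases** (illustrative first dose 20 March 2019):

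| Recorded start | Recorded end | Start used | In the AE tables? |
|---|---|---|---|
| day missing, March 2019 | 10 March 2019 | 21 March 2019 | yes, though it ended 10 days before dosing |
| 2019 only | 10 March 2019 | 21 March 2019 | yes, same error |
| day missing, February 2019 | any | 15 February 2019 | no |
| 5 March 2019 | any | 5 March 2019 | no |

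The fault therefore needs a partial start date. In a second example, with first dose on 31 March, an AE recorded only as March is given 1 April, outside its recorded month.

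**3. How often a partial pre-dose date is moved.** Assume onset is uniform over days -28 to -1.

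- Day missing: for first dose on day d of a month, the share moved is min(d - 1, 28)/28, which is 0% for d = 1 and 100% for d of 29 or more. Summed over the days of a month, this gives 16.5 (31 days), 15.5 (30), 13.5 (28) and 14.5 (29). A common year gives 7 × 16.5 + 4 × 15.5 + 13.5 = 191 and a leap year 192. Over four years, (3 × 191 + 192)/1461 = 52.4%.
- Day and month missing: the share is min(k - 1, 28)/28 for first dose on day k of the year. A common year gives 13.5 + 337 = 350.5 and a leap year 351.5. Over four years, (3 × 350.5 + 351.5)/1461 = 96.0%.
- Complete date: 0%.

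These shares apply only to pre-dose AEs whose date is already partial.

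**4. Improvement records.** Suppose a Grade 3 AE starts on Day -10 and improves to Grade 2 on Day 15. Protocol 8.1.1 creates a Grade 2 entry starting on Day 15. SAP 2.8.1 counts it because Day 15 is after Day 1. Under protocol 10.4.2 nothing started or became worse, so it should not count. An improvement from Grade 4 to Grade 3 would also reach the Grade 3/4 tables. True worsening needs no extra rule, because protocol 8.1.1 already gives it a new record and date.

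**5. Size.** One patient wrongly counted in a term adds 1/40 = 2.5 points. The documents do not give the number of such patients. For an assumed range of 1 to 4 in a term with no true on-treatment cases, the reported rate would be 1/40 = 2.5% to 4/40 = 10.0%. SAP 2.8.1 also has a registry table of non-serious events with a 5% threshold, which is 0.05 × 40 = 2 patients. One wrongly counted patient could move a term from 1 to 2 and so into that table.

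**The case against.** The strongest reply is that this hardly ever happens. The first case needs onset between consent and Day 1, a partial start date, and an end date known well enough to prove the event was over. Conditions already present at consent go to medical history, AEs are sought at each visit (protocol 8.1.1), and missing values are queried (protocol 9.4). The second case needs a Grade 3/4 event in screening in a patient who is still treated, despite exclusion criteria 5 and 16. A patient counts once per AE category, so another on-treatment event in the same term hides the error. The bias only overstates incidence, in a descriptive study without testing. All of this stands and keeps the point small. It does not justify counting an event whose end date precedes dosing, and the SAP states no such intention.

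The protocol's definition could also be said to govern, since SAP section 4 declares no change. That makes this a gap in wording rather than a deliberately different definition. Tables programmed from the SAP text would still include the records.

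A reader might infer four stronger things that the documents do not support:

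- *Events that ended before dosing also enter through complete recorded dates.* They do not (step 2). The improvement records concern events still ongoing after Day 1.
- *The rule attributes these events to everolimus.* Causality is assessed separately by the investigator for each AE, and suspected-relationship tables are separate. Imputing a date changes neither assessment.
- *The 52.4% and 96.0% are effect sizes.* They are conditional on a partial date. The 28-day window is itself an assumption, because protocol 7.1.2 says that the 28-day screening period does not apply to the consent process.
- *Confidence intervals would be distorted.* SAP 2.8.1 plans numbers and percentages for AEs, with no intervals.

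**Conclusion.** The point holds in this limited form. As written, SAP 5.1.2 together with 2.1.1.6 and 2.8.1 counts as on-treatment an AE with a partial start date and a known end before first dose, which conflicts with protocol 10.4.1. SAP 2.8.1 also counts improvement records of pre-dose Grade 3/4 events, which conflicts with protocol 10.4.2. The effect is upward only and probably very small: at most 2.5 points per affected patient per preferred term, and nothing if that patient has another on-treatment event in the term. The number of affected records is unknown. The conclusion rests on reading the SAP rules literally, with no unstated end-date or grade check in the programs. It should be corrected because the rule gives a demonstrably wrong result on the primary endpoint and the repair is simple. It does not threaten the study's overall safety conclusions.

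**What to change.** Add to SAP 5.1.2:

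> If the AE end date is known and is before the first dose date, the event is classified as pre-treatment. An imputed start date may not be later than a known end date and may not fall outside the recorded month.

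Under this text, an AE that ended on the day of first dose, or whose end is unknown, still counts as on-treatment, so the cautious convention is kept where onset really is uncertain.

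Add to SAP 2.8.1:

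> A CRF record that only documents improvement of an AE that was ongoing at first dose, with a grade no higher than the last grade recorded before first dose, is not treatment-emergent. Any later worsening, or recurrence after resolution, is counted.

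The last sentence matters. A simple same-or-lower-grade exclusion would hide an event that improves from Grade 3 to Grade 2 and returns to Grade 3 on treatment.

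The cost is a small programming change and no new data. SAP 2.7.1 already reports findings at database lock, so the AE tables may need a rerun and the change should be dated and recorded as such. A sensible first step is to list AE records whose imputed start is later than their end, and improvement entries that continue a pre-dose AE. If there are none, the study report can say so and the tables stand.
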